Dose adjustments made to either SEP-363856 or quetiapine XR will be done in a blinded fashion. Dose increases can be made no more frequently than weekly to the next higher dose level beginning on Day 8, if the response to the previous dose level is not adequate and there are no significant tolerability problems, based on Investigator judgement. Increases in dose will occur at regularly scheduled study visits when possible. However, dose increases between regularly scheduled visits may occur (as long as the subject has been taking the previous dose level for at least 7 days). If a dose increase is performed between regularly scheduled visits, subjects will be required to return to the clinic at an unscheduled visit for drug dispensation.

Dose reductions can be made to the next lower dose level at any time (at least 1 day apart) beginning on Day 8 for tolerability issues as judged by the Investigator. If a dose reduction is needed between study visits, subjects will be asked to return to the clinic for an unscheduled visit for drug dispensation.

For subjects who have received study drug and who prematurely discontinue from the study treatment, every effort should be made to complete the final evaluation procedures within 48 hours of the last study drug dose at the early termination (ET) visit.

Follow-up Period (1 week):

Subjects who discontinue early from the study or complete the study will be required to complete the Follow-up Visit 7 days (\pm 2 days) post last dose of study drug.

Number of Subjects (planned): 300 subjects

Diagnosis and Criteria for Subject Inclusion:**Inclusion criteria:**

The main inclusion criteria include, but are not limited to the following:

- Male or female subject between 18 to 65 years of age (inclusive) at the time of consent.
- Subject meets DSM-5 criteria for a diagnosis of schizophrenia as established by clinical interview at Screening (using the DSM-5 as a reference and confirmed using the SCID-CT). The time since the subject's diagnosis must be ≥ 1 year prior to Screening.
- Subject must have a CGI-S score ≤ 4 at Screening and Baseline.
- Subject must have a PANSS total score ≤ 80 at Screening and Baseline.
- Subject is judged to be clinically stable (i.e., no evidence of an acute exacerbation) by the Investigator for at least 8 weeks prior to Screening.

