6.3. Other Efficacy Endpoints

- Changes from Baseline in:
 - PANSS total score and subscale scores (positive, negative, and general psychopathology)
 - CGI-S score
 - BNSS total score
 - MADRS total score
 - ESS total score
 - BACS composite score
 - UPSA-B total score
 - SLOF total and subscale scores
 - EQ-5D-5L visual analog scale (VAS), index score and dimension score
 - MSQ score
- Time to relapse, rate of relapse, and frequency of hospitalization due to relapse. Relapse will be defined as the earliest occurrence of any of the following:
 - Worsening of > 30% PANSS total score from Baseline and CGI-S > 3
 - Hospitalization for worsening of psychosis

- Emergence of suicidal ideation, homicidal ideation and/or risk of harm to self or others
- Discontinuation from the study due to exacerbation of the underlying illness of schizophrenia
- Time to all cause discontinuation from the study
- Change from Baseline in tobacco use
- Plasma cotinine concentrations

6.4.

CCI

[figure not shown]

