6.7. COMMON CALCULATIONS

For quantitative measurements, change from Baseline will be calculated as:

- Test Value at Visit X – Baseline Value

For PANSS Total score, percentage change from Baseline will be calculated as:

- $(\text{Test Value at Visit X} - \text{Baseline Value}) \times 100 / (\text{Baseline Value} - 30)$

For other quantitative measurements, percentage change from Baseline will be calculated as:

- $(\text{Test Value at Visit X} - \text{Baseline Value}) \times 100 / \text{Baseline Value}$

Document: CCI

Author: PPD

Version Number: 0.6

Version Date: 30JAN2023

Template No.: CS_TP_BS016 Revision 6

Reference: CS_WI_BS005

Effective Date: 02Dec2019

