16.1. PANSS

The PANSS (Positive and Negative Syndrome Scale) is an interview-based measure of the severity of psychopathology in adults with psychotic disorders and comprises 30 items and 3 subscales. The positive subscale assesses hallucinations, delusions, and related symptoms (7 items); the negative subscale assesses emotional withdrawal, lack of motivation, and related symptoms (7 items); and the general psychopathology subscale assesses other symptoms such as anxiety, somatic concern, and disorientation (16 items). An anchored Likert scale from 1 to 7 (1 = absent, 7 = extreme, with values of 2 and above indicating the presence of progressively more severe symptoms) is used to score each item.

Individual items are summed to derive the following scores:

- Total score = sum of all 30 items. Total score ranges from 30 to 210.
- Subscale scores = sum of items within each of the following subscales:
 - Positive subscale: delusions, conceptual disorganization, hallucinatory behavior, excitement, grandiosity, suspiciousness/persecution, hostility. The subscale score ranges from 7 to 49.
 - Negative subscale: blunted affect, emotional withdrawal, poor rapport, passive/apathetic social withdrawal, difficulty in abstract thinking, lack of spontaneity and flow of conversation, stereotyped thinking. This subscale score ranges from 7 to 49.
 - General psychopathology subscale: somatic concern, anxiety, guilt feelings, tensions, mannerisms and posturing, depression, motor retardation, uncooperativeness, unusual thought content, disorientation, poor attention, lack of judgment and insight, disturbance of volition, poor impulse control, preoccupation, active social avoidance. This subscale score ranges from 16 to 112.

Document: CCI

Author: PPD

Version Number: 0.6

Version Date: 30JAN2023

Template No.: CS_TP_BS016 Revision 6

Reference: CS_WI_BS005

Effective Date: 02Dec2019

- Marder factor scores = sum of items within each of the following factors (Marder, Davis, Chouinard. 1997):
 - Negative symptoms: blunted affect, emotional withdrawal, poor rapport, passive/apathetic social withdrawal, lack of spontaneity and flow of conversation, motor retardation, active social avoidance. This Marder factor score ranges from 7 to 49.
 - Positive symptoms: delusions, hallucinatory behavior, grandiosity, suspiciousness/persecution, stereotyped thinking, somatic concern, unusual thought content, lack of judgment and insight. This Marder factor score ranges from 8 to 56.

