16.1.6. PROPORTION OF SUBJECTS WHO ACHIEVE A RESPONSE

PANSS response is defined as a 20% or greater improvement (i.e. decrease) in PANSS total score from Baseline.

The percent change in PANSS total score from Baseline will be calculated by:

$$\frac{\text{PANSS total score at a visit or the Week 52 LOCF endpoint} - \text{PANSS total score at Baseline}}{\text{PANSS total score at Baseline} - 30} \times 100\%$$

For each subject, the responder indicator will be set to Y if the percent change is negative and the magnitude is equal to or greater than 20%. The indicator will be set to N if the percentage is negative but the magnitude is less than 20% or the percentage is non-negative. The indicator will be set to missing if the percentage is missing.

In addition, PANSS response defined by two more stringent thresholds will be assessed; that is, having a 30% or greater and 50% or greater improvement in PANSS total score from Baseline.

PANSS response at all three thresholds will be derived for all post-Baseline time points.

PANSS response at each scheduled visit and at the LOCF endpoint will be analyzed using a logistic regression model with responder indicator as the dependent variable and include factors for treatment and geographic region, and include Baseline PANSS total score as a covariate. The Number Needed to Treat (NNT) will be provided:

- The NNT for each SEP-363856 group will be derived as:

Document: CCI

Author: PPD

Version Number: 0.6

Version Date: 30JAN2023

Template No.: CS_TP_BS016 Revision 6

Reference: CS_WI_BS005

Effective Date: 02Dec2019

- $$\text{NNT} = \frac{1}{\text{Risk Reduction (RR)}} = \frac{1}{\text{PANSS Response Rate}_{\text{SEP-363856}} - \text{PANSS Response Rate}_{\text{Quetiapine XR}}}$$
- Only positive NNT results will be presented. The NNT results will be provided in whole numbers with any fractional values rounded up to the nearest whole number. The 95% CI of NNT will also be presented and are computed by taking the reciprocal of the 95% CI lower and upper bounds of the RR when both bounds are positive. The lower confidence limit will be rounded down to the largest whole number that is less than the computed estimate, and the upper confidence limit will be rounded up to the smallest whole number that is greater than the computed estimate.

The number and percentage of subjects who achieve a PANSS response will also be summarized descriptively by treatment group and visit.

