16.2.12. RELAPSE

Relapse is defined as the earliest occurrence of any of the following:

- Worsening of >30% PANSS total score from Baseline (Day 1) and a CGI-S score >3
- Hospitalization for worsening of psychosis
- Emergence of suicidality, homicidality and/or risk of harm to self or others
- Discontinuation from the study due to exacerbation of the underlying illness of schizophrenia.

PANSS and CGI-S assessments taken at both scheduled and unscheduled visits will be considered when identifying the relapse event. The percent change in PANSS total score from Baseline will be calculated as described in [Section 16.1.6](#). Occurrence of hospitalization for worsening of psychosis will be identified by medical review of the data collected on the “*Psychiatric Hospitalization*” CRF page as well as the SAEs prior to database lock. Emergence of suicidality, homicidality, and/or risk of harm to self or others will be identified as outlined in [APPENDIX 11](#). Discontinuation from the study due to exacerbation of the underlying illness of schizophrenia will be identified as an AE included in the SMQ search listed in [APPENDIX 13 that has action taken = “Drug Withdrawn”](#).

The evaluation period for relapse will be from the day of the first dose of study medication to 2 days after the day of the last dose of study medication.

The date of relapse is defined as the earliest of: the start date of the assessment at which the qualifying PANSS and CGI-S data were collected, the date of hospital admission for worsening of psychosis, the

Document: **CCI**

Author: **PPD**

Version Number: 0.6

Version Date: 30JAN2023

Template No.: CS_TP_BS016 Revision 6

Reference: CS_WI_BS005

Effective Date: 02Dec2019

date of the assessment at which a qualifying C-SSRS event is identified, the start date of the qualifying adverse event for the second and third criteria, and the last dose date for the fourth criterion.

Time-to-relapse (in days) is defined as the date of relapse – the first dose date + 1. Subjects completing/discontinuing from the study without meeting the criteria for relapse will be censored on 2 days after the last dose of study medication.

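### Relapse criterion 1 cannot separate relapse from fluctuation within the entry limits for subjects who enter at CGI-S 4 with a Baseline PANSS of 68 or below

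*SAP*

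**What the plan says.** Entry sets two ceilings: "Subject must have a CGI-S score ≤ 4 at Screening and Baseline" and "Subject must have a PANSS total score ≤ 80 at Screening and Baseline" (Protocol Synopsis, repeated as inclusion criteria 7 and 8 in Section 8.1). There is no PANSS minimum.

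The first of four relapse criteria in Protocol 6.3 is "Worsening of > 30% PANSS total score from Baseline and CGI-S > 3". SAP 16.2.12 repeats it as "Worsening of >30% PANSS total score from Baseline (Day 1) and a CGI-S score >3". The protocol gives no denominator for the percentage. The SAP does: "The percent change in PANSS total score from Baseline will be calculated as described in" Section 16.1.6, where the change is divided by the Baseline total minus 30. SAP 6.7 gives the same rule for every percentage change in PANSS total. SAP 3.7, which lists changes from the protocol, covers only the efficacy and per protocol populations.

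Scheduled and unscheduled PANSS and CGI-S ratings both count, and the earliest qualifying one fixes the relapse date. Neither document asks for a rise in CGI-S, an absolute PANSS level or a confirming assessment. The manual review in Protocol 15.3.5 applies the same criteria. The SAP assigns medical review to psychiatric hospitalization (16.2.12) and to suicide and self-injury events (Appendix 11), not to criterion 1.

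Relapse feeds a crude rate in the efficacy population, Kaplan-Meier estimates and a log-rank test between arms (SAP 16.2.12). Protocol 15.3.5 calls all efficacy analyses exploratory.

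**The concern.** CGI-S 4 is both the highest score allowed at entry and the lowest score above 3. For a subject who enters at 4, the CGI-S part is met before the first dose and adds nothing to the PANSS part. The PANSS part then has to carry the criterion alone, and subtracting 30 from the denominator makes the required rise small for a stable population with low totals. A subject can be recorded as relapsed while still within the PANSS and CGI-S limits that admitted them.

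Time to relapse and relapse rate answer the maintenance-efficacy objective. If ordinary fluctuation counts as relapse, the rate is too high in both arms. Where such events occur equally often in the two arms, they also tend to obscure a real difference.

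**Working it through.** **Inputs.** Entry limits: CGI-S 4 or less, PANSS 80 or less (Protocol 8.1). Criterion 1 and its denominator: SAP 16.2.12, 16.1.6 and 6.7. PANSS floor: "Total score ranges from 30 to 210" (SAP 16.1). Nine scheduled post-Baseline PANSS visits: Weeks 1, 4, 8, 16, 24, 32, 40, 48 and 52 (SAP 16.1.1.1). The documents give no relapse rate, event count or power, so there is no plan figure to reproduce.

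**Step 1, CGI-S part.** Entering at 4: 4 > 3 holds with no change. Entering at 3 or below: the subject must worsen to at least 4, so this part still works.

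**Step 2, PANSS part.** For Baseline B, the smallest qualifying whole-number rise is the first integer above 0.3 × (B − 30) under the SAP, or above 0.3 × B on the raw total. The two thresholds differ by 0.3 × 30 = 9 points at every Baseline.

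| B | 0.3 × (B − 30) | SAP rise | SAP score | 0.3 × B | Raw rise | Raw score |
|---|---|---|---|---|---|---|
| 40 | 3.0 | 4 | 44 | 12.0 | 13 | 53 |
| 50 | 6.0 | 7 | 57 | 15.0 | 16 | 66 |
| 60 | 9.0 | 10 | 70 | 18.0 | 19 | 79 |
| 61 | 9.3 | 10 | 71 | 18.3 | 19 | 80 |
| 62 | 9.6 | 10 | 72 | 18.6 | 19 | 81 |
| 68 | 11.4 | 12 | 80 | 20.4 | 21 | 89 |
| 69 | 11.7 | 12 | 81 | 20.7 | 21 | 90 |
| 80 | 15.0 | 16 | 96 | 24.0 | 25 | 105 |

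**Step 3, overlap with entry.** With CGI-S unchanged at 4, a score of 80 or less qualifies for every Baseline up to 68 under the SAP rule, and up to 61 on the raw total. Baselines 69 to 80 must exceed 80. The minus-30 rule widens the overlap but does not create it. At a Baseline of exactly 30 the SAP formula divides by zero, which requires every item to be scored absent.

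**Step 4, how many subjects.** The documents do not say. Assume a normal Baseline PANSS within 30 to 80, mean 55 to 70 and SD 6 to 10. The share at 68 or below then runs from about 42% to 99%, and at 61 or below from about 8% to 86%. These shares cover the PANSS part only; those affected must also enter at CGI-S 4.

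**Step 5, does retention matter?** Assume a 5% chance of a spurious event at each of nine visits in both arms, with dropout after each visit of 3% in one arm and 12% in the other. The chance of still being at risk at the next visit is 0.95 × 0.97 = 0.9215 and 0.95 × 0.88 = 0.836. The crude rate is 0.05 × (1 − r^9)/(1 − r), which gives 33% and 24%. A simulated log-rank test on the same inputs rejected 5.1% of the time. Retention therefore shifts the crude rate but not the log-rank test.

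**The case against.** The strongest reply is that little depends on this. Relapse is one of many other efficacy endpoints, p-values are nominal (SAP 7.4), the primary endpoint is adverse event incidence, and the sample size does not rest on relapse. That stands, and it limits how much weight the point can carry.

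Several stronger readings are tempting, and the documents do not support them.

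- A reader might infer that minus-30 is a mistake or a hidden departure from the protocol. It removes the scale floor, is the SAP's general rule and is cross-referenced openly for relapse. The protocol left the denominator open.
- A reader might infer that the PANSS and CGI-S ceilings define stability, so that relapse below them is contradictory. Stability has its own requirements: no acute exacerbation for 8 weeks, unchanged antipsychotic treatment and no recent psychiatric hospitalization. Worsening against a subject's own Baseline can be real below a ceiling.
- A reader might infer that spurious relapses cluster in the mildest subjects. The smallest rises occur at Baselines of 40 to 50, a mean item score of 40/30 = 1.3 to 50/30 = 1.7 where 1 means absent. Such subjects may well enter at CGI-S 3 or below and would have to worsen to 4. No joint distribution is given.
- A reader might simulate rating noise and quote large rates. With no true change, CGI-S fixed at 4, all nine visits attended and an assumed SD of 5, the chance of at least one event is about 69%, 49% and 30% at Baselines 45, 55 and 65. With SD 3 it is 49%, 19% and 4%. With SD 5 and four visits it is 54%, 35% and 19%. The SD has no source in the documents, and fixing CGI-S at 4 is the worst case.

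**Conclusion.** The point holds for part of the population: subjects who enter at CGI-S 4 with a Baseline PANSS of 68 or below (61 or below on the raw total). For them a single rating can count as relapse with CGI-S unchanged and PANSS still at 80 or less. The thresholds follow from the text and need no assumption.

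Such events raise the relapse rate and the Kaplan-Meier probability of relapse. Dilution of the comparison between arms is the expected direction if they are unrelated to treatment, but its amount has not been calculated. The crude rate also depends on how long each arm is retained. The log-rank test does not, given an equal chance of a spurious event per assessment and independent dropout.

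The overall size is unknown. The primary safety endpoint and the sample size are unaffected. The point is worth acting on because the remedy is cheap, but it is not a condition for a sound primary analysis.

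**What to change.** Keep the protocol definition of relapse as the main one.

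- In SAP 16.2.12, pre-specify a supplementary analysis of relapse rate and time to relapse in which criterion 1 also requires a CGI-S increase of at least 1 point from Baseline at the same assessment. A subject entering at 4 must then reach 5, outside the entry limit. Nothing changes for those entering at 3 or below, who already need a rise.
- Report the number of relapses that qualify by criterion 1 alone, split by Baseline CGI-S (4 versus 3 or below). This shows how much the issue matters in the actual data.
- State in SAP 3.7 that the relapse percentage uses Baseline minus 30, which the protocol does not specify, and show the raw-total version as a sensitivity analysis. The raw total alone would not be enough, since overlap remains up to Baseline 61.

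The cost is one extra derivation and set of tables on data already collected. The relapse rate will be lower in the supplementary analysis, and true relapses rated CGI-S 4 throughout would be caught there only by criteria 2 to 4.

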In case the model above fails to converge, a spatial exponential covariance structure and a spatial power covariance structure will be assumed sequentially. The first covariance structure to yield convergence will be used in the analysis. These analyses will be based on the observed data only. Missing data will not be imputed.

Sensitivity analyses may be conducted to assess the impact of missing data on the PANSS total score and CGI-S score analysis results by deviating away from the MAR assumption; however, all efficacy analyses are exploratory in this safety study.

Relapse

Relapse will be identified programmatically and manual data review using the pre-defined criteria (specified below). The rate of relapse will be calculated as the proportion of subjects with

a relapse in the 52-week period out of the efficacy population, along with the 95% confidence interval. The time-to-relapse will be summarized descriptively and will also be presented by a Kaplan-Meier plot, with log rank test statistic.

Relapse will be defined as the earliest occurrence of any of the following:

- Worsening of > 30% PANSS total score from Baseline (Day 1) and a CGI-S score > 3.
- Hospitalization for worsening of psychosis.
- Emergence of suicidality, homicidality and/or risk of harm to self or others.
- Discontinuation from the study due to exacerbation of the underlying illness of schizophrenia.

The frequency of hospitalization due to relapse will be summarized descriptively by treatment.

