Effective Date: 02Dec2019

Akathisia		Dyskinesia		Dystonia		Parkinson-like	
PT	Code	PT	Code	PT	Code	PT	Code
-	-	-	-	-	-	Parkinson's disease	10061536
-	-	-	-	-	-	Parkinson's disease psychosis	10074835
-	-	Pharyngeal dyskinesia	10070912	-	-	-	-
-	-	-	-	Pharyngeal dystonia	10081226	-	-
-	-	-	-	Pleurothotonus	10035628	-	-
-	-	-	-			Propulsive gait	10082328
-	-	Protrusion tongue	10037076	-	-	-	-
-	-	Rabbit syndrome	10068395	-	-	-	-
-	-	Respiratory dyskinesia	10057570	-	-	-	-
-	-	-	-	-	-	Resting tremor	10071390
-	-	-	-	Spasmodic dysphonia	10067672	-	-
-	-	Tardive dyskinesia	10043118	-	-	-	-
-	-	-	-	Torticollis	10044074	-	-
-	-	-	-	Trismus	10044684	-	-
-	-	-	-	Writer's cramp	10072249	-	-
-	-	Abnormal involuntary movement scale	10075002	-	-	-	-
-	-	-	-	-	-	Action tremor	10072413
-	-	-	-	Blepharospasm	10005159		
-	-	-	-	-	-	Bradyphrenia	10050012
-	-	Chronic tic disorder	10076661	Chronic tic disorder	10076661	-	-
-	-	Complex tic	10076663	Complex tic	10076663	-	-

Document: CCI

Author: PPD

Version Number: 0.6

Version Date: 30JAN2023

Template No.: CS_TP_BS016 Revision 6

Reference: CS_WI_BS005

Effective Date: 02Dec2019

Akathisia		Dyskinesia		Dystonia		Parkinson-like	
PT	Code	PT	Code	PT	Code	PT	Code
-	-	Drooling	10013642	Drooling	10013642	Drooling	10013642
-	-	-	-	-	-	Dysphonia	10013952
Extrapyramidal disorder	10015832	Extrapyramidal disorder	10015832	Extrapyramidal disorder	10015832	Extrapyramidal disorder	10015832
-	-	-	-	Facial spasm	10063006	-	-
-	-	-	-	-	-	Fine motor skill dysfunction	10076288
-	-	-	-	-	-	Gait disturbance	10017577
-	-	-	-	Gait inability	10017581	-	-
Hyperkinesia	10020651	-	-	-	-	-	-
Hyperkinesia neonatal	10020652	-	-	-	-	-	-
-	-	-	-	-	-	Hypokinesia	10021021
-	-	-	-	-	-	Hypokinesia neonatal	10021022
-	-	-	-	-	-	Laryngeal tremor	10078751
-	-	-	-	Laryngospasm	10023891	-	-
-	-	-	-	-	-	Micrographia	10057333
-	-	-	-	-	-	Mobility decreased	10048334
Motor dysfunction	10061296	Motor dysfunction	10061296	Motor dysfunction	10061296	Motor dysfunction	10061296
Movement disorder	10028035	Movement disorder	10028035	Movement disorder	10028035	Movement disorder	10028035
-	-	Muscle twitching	10028347	-	-	-	-
-	-	-	-	Muscle contractions involuntary	10028293	-	-
-	-	-	-	Muscle spasms	10028334	-	-
-	-	-	-	Muscle spasticity	10028335	-	-
-	-	-	-	Muscle tightness	10049816	-	-

Document: CCI

Author: PPD

Version Number: 0.6

Version Date: 30JAN2023

Template No.: CS_TP_BS016 Revision 6

Reference: CS_WI_BS005

Effective Date: 02Dec2019

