APPENDIX 11. IDENTIFICATION OF SUICIDALITY, HOMICIDALITY, AND/OR RISK OF HARM TO SELF OR OTHERS

Condition	Data Source	Criteria
Suicidality or Risk of Harm to Self	Adverse events	
 AEs with preferred term of “Assisted suicide”, “Completed suicide”, “Suicide attempt”, “Suspected suicide”, or “Suspected suicide attempt” Medical review of all AEs contained in the MedDRA SMQ of “Suicide/self-injury (SMQ)”
	C-SSRS	
 C-SSRS findings of at least one occurrence of suicidal ideation (Item 4 and/or Item 5) or at least one occurrence of suicidal behavior C-SSRS findings of self-injurious behavior, defined as a “Yes” answer to the following question in the Suicidal Behavior section: Has subject engaged in Non-Suicidal Self-Injurious behavior?
Homicidality or Risk of Harm to Others	Adverse events	
 AEs with preferred term of “Aggression”, “Anger”, “Antisocial behaviour”, “Belligerence”, “Defiant behaviour”, “Homicide”, “Homicidal Ideation”, “Hostility”, “Physical abuse”, “Physical assault”, or “Violence-related symptom” contained in the MedDRA SMQ of “Hostility/aggression (SMQ)” AEs with a verbatim term that contains text of “homicid*”, “kill*”, or “murder*”.

Document: CCI

Author: PPD

Version Number: 0.6

Version Date: 30JAN2023

Template No.: CS_TP_BS016 Revision 6

Reference: CS_WI_BS005

Effective Date: 02Dec2019

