Hallucination, olfactory	10019072 PT	Narrow A	0	Active	10.1	10.1
Hallucination, synaesthetic	10062824 PT	Narrow A	0	Active	10.1	10.1
Hallucination, tactile	10019074 PT	Narrow A	0	Active	10.1	10.1
Hallucination, visual	10019075 PT	Narrow A	0	Active	10.1	10.1
Hallucinations, mixed	10019079 PT	Narrow A	0	Active	10.1	10.1
Hypnagogic hallucination	10020927 PT	Narrow A	0	Active	10.1	10.1
Hypnopompic hallucination	10020928 PT	Narrow A	0	Active	10.1	10.1
Hysterical psychosis	10062645 PT	Narrow A	0	Active	10.1	10.1
Ideas of reference	10021212 PT	Narrow A	0	Active	10.1	10.1
Illusion	10021403 PT	Narrow A	0	Active	10.1	10.1
Jealous delusion	10023164 PT	Narrow A	0	Active	10.1	10.1
Loose associations	10024825 PT	Narrow A	0	Active	10.1	10.1
Mixed delusion	10076429 PT	Narrow A	0	Active	18.0	18.0
Neologism	10028916 PT	Narrow A	0	Active	10.1	10.1
Neuroleptic-induced deficit syndrome	10075295 PT	Narrow A	0	Active	17.1	17.1
Paranoia	10033864 PT	Narrow A	0	Active	10.1	10.1
Paranoid personality disorder	10033869 PT	Narrow A	0	Active	10.1	10.1
Parkinson's disease psychosis	10074835 PT	Narrow A	0	Active	17.0	17.0
Paroxysmal perceptual alteration	10063117 PT	Narrow A	0	Active	10.1	10.1
Persecutory delusion	10034702 PT	Narrow A	0	Active	10.1	10.1
Postictal psychosis	10070669 PT	Narrow A	0	Active	13.1	13.1
Post-injection delirium sedation syndrome	10072851 PT	Narrow A	0	Active	16.0	16.0
Posturing	10036437 PT	Narrow A	0	Active	10.1	10.1
Psychosis postoperative	10065617 PT	Narrow A	0	Active	10.1	10.1
Psychotic behaviour	10037249 PT	Narrow A	0	Active	10.1	10.1
Psychotic disorder	10061920 PT	Narrow A	0	Active	10.1	10.1
Psychotic disorder due to a general medical condition	10061921 PT	Narrow A	0	Active	10.1	10.1
Reactive psychosis	10053632 PT	Narrow A	0	Active	10.1	10.1
Rebound psychosis	10074833 PT	Narrow A	0	Active	17.0	17.0

Document: CCI

Author: PPD

Version Number: 0.6

Version Date: 30JAN2023

Template No.: CS_TP_BS016 Revision 6

Reference: CS_WI_BS005

Effective Date: 02Dec2019

Schizoaffective disorder	10039621	PT	Narrow	A	0	Active	10.1	10.1
Schizoaffective disorder bipolar type	10068889	PT	Narrow	A	0	Active	12.0	12.0
Schizoaffective disorder depressive type	10068890	PT	Narrow	A	0	Active	12.0	12.0
Schizophrenia	10039626	PT	Narrow	A	0	Active	10.1	10.1
Schizophreniform disorder	10039647	PT	Narrow	A	0	Active	10.1	10.1
Schizotypal personality disorder	10039651	PT	Narrow	A	0	Active	10.1	10.1
Senile psychosis	10039987	PT	Narrow	A	0	Active	10.1	10.1

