Logorrhea	10024796 PT	Broad	A	0	Active	10.1	10.1
Magical thinking	10025429 PT	Broad	A	0	Active	10.1	10.1
Major depression	10057840 PT	Broad	A	0	Active	10.1	10.1
Malignant catatonia	10080149 PT	Broad	A	0	Active	20.1	20.1
Mania	10026749 PT	Broad	A	0	Active	10.1	10.1
Mutism	10028403 PT	Broad	A	0	Active	10.1	10.1
Obsessive rumination	10056264 PT	Broad	A	0	Active	10.1	10.1
Paralogism	10077175 PT	Broad	A	0	Active	18.1	18.1
Perseveration	10034703 PT	Broad	A	0	Active	10.1	10.1
Poverty of speech	10036467 PT	Broad	A	0	Active	10.1	10.1
Poverty of thought content	10036468 PT	Broad	A	0	Active	10.1	10.1
Presenile dementia	10036631 PT	Broad	A	0	Active	10.1	10.1
Pressure of speech	10036649 PT	Broad	A	0	Active	10.1	10.1
Senile dementia	10039966 PT	Broad	A	0	Active	10.1	10.1
Social avoidant behaviour	10041243 PT	Broad	A	0	Active	10.1	10.1
Speech disorder	10041466 PT	Broad	A	0	Active	10.1	10.1
Suspiciousness	10042635 PT	Broad	A	0	Active	10.1	10.1
Tachyphrenia	10064805 PT	Broad	A	0	Active	10.1	10.1
Thinking abnormal	10043431 PT	Broad	A	0	Active	10.1	10.1
Vascular dementia	10057678 PT	Broad	A	0	Active	10.1	10.1
Verbigeration	10047313 PT	Broad	A	0	Active	10.1	10.1
Withdrawal catatonia	10081010 PT	Broad	A	0	Active	21.0	21.0

Document: CCI

Author: PPD

Version Number: 0.6

Version Date: 30JAN2023

Template No.: CS_TP_BS016 Revision 6

Reference: CS_WI_BS005

Effective Date: 02Dec2019

Statistical Analysis Plan - Final Statistical Analysis Plan 30Jan2023 - SAP or PK-PD Sections Thereof - 30-Jan-2023

Electronic Signature Manifestation

This page is a manifestation of the electronic signature(s) used in compliance with the organization's electronic signature policies and procedures.

Signer Full Name	Meaning of Signature	Date and Time
PPD	Document Approval (I certify that I have the education, training and experience to perform this task)	30 Jan 2023 15:26:03 UTC
PPD	Document Approval (I certify that I have the education, training and experience to perform this task)	30 Jan 2023 15:27:52 UTC
PPD	Document Approval (I certify that I have the education, training and experience to perform this task)	30 Jan 2023 15:34:21 UTC
PPD	Document Approval (I certify that I have the education, training and experience to perform this task)	30 Jan 2023 15:34:25 UTC
PPD	Document Approval (I certify that I have the education, training and experience to perform this task)	30 Jan 2023 15:37:07 UTC

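### Relapse criterion 4 counts any withdrawal on a 130-term psychosis list as a schizophrenia exacerbation, and the SAP names no medical review to confirm it

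*SAP*

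**What the plan says.** Protocol 15.3.5 sets the method for the relapse endpoint as a whole: "Relapse will be identified programmatically and manual data review using the pre-defined criteria".

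SAP 16.2.12 and its appendices then give a rule for each criterion.

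- Criterion 1 (PANSS and CGI-S) is a numeric threshold.
- Criterion 2 (hospitalization) is reviewed: "Occurrence of hospitalization for worsening of psychosis will be identified by medical review of the data collected on the" psychiatric hospitalization CRF page, together with the SAEs, before database lock.
- Criterion 3 (suicidality, homicidality, risk of harm) follows Appendix 11. Part of it is reviewed: "Medical review of all AEs contained in the MedDRA SMQ of" suicide/self-injury. The hostility/aggression SMQ is cut down to named preferred terms. The remaining rules, including those on the C-SSRS, are fixed.
- Criterion 4 is identified by rule: "Discontinuation from the study due to exacerbation of the underlying illness of schizophrenia will be identified as an AE included in the SMQ search" of Appendix 13, with an action taken of Drug Withdrawn. No review is mentioned.

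Appendix 13 reproduces the psychosis and psychotic disorders SMQ with both narrow and broad terms. SAP 16.2.12 does not limit the search to either. SAP 3.7, which lists changes from the protocol, has three entries. All concern the efficacy and per protocol populations; none concerns relapse.

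**The concern.** The criterion is about cause: the subject left because schizophrenia worsened. The rule shows only that drug was stopped for an AE on a psychosis list. Protocol 13.1 says that subjects who stop study drug also leave the study, so Drug Withdrawn is a fair stand-in for discontinuation. It says nothing about why the AE arose.

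Criterion-4 events enter the relapse rate, the Kaplan-Meier estimates and the log-rank test, through which the SAP addresses the maintenance-efficacy objective. A subject withdrawn for a drug effect or a mood episode, and meeting no other criterion, should be censored 2 days after the last dose. Under the rule as written, that subject becomes a relapse dated to the last dose. A tolerability failure would then be reported as loss of efficacy.

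**Working it through.** The documents give no relapse rate, event count or power for this endpoint, so there is no planned figure to reproduce. The check is a count of the list, a comparison of rules and a per-subject scale.

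1. **Size of the list.** Counting Appendix 13 row by row gives 78 narrow + 52 broad = 130 preferred terms, with 130 distinct codes. The broad share is 52/130 = 40%.

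2. **Terms that need not be an exacerbation of schizophrenia.**
   - Broad: "Major depression", Bipolar I disorder, Alcohol withdrawal syndrome and "Speech disorder". Protocol exclusion 2 itself treats major depressive and bipolar I disorder as diagnoses other than schizophrenia.
   - Narrow: "Neuroleptic-induced deficit syndrome", which is drug-induced by its name, and Post-injection delirium sedation syndrome. Limiting the search to narrow scope would therefore not cure the problem.

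3. **Overlap with the SAP's own extrapyramidal list (Appendix 4).** Three terms are on both lists: "Bradyphrenia" (broad in Appendix 13), Posturing and Parkinson's disease psychosis (both narrow). One withdrawal coded to any of these could be summarized as an extrapyramidal AE and also scored as a relapse.

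4. **Comparison of rules.** Criterion 2 has medical review. The two SMQ searches under criterion 3 have either medical review or a selection of terms. Criterion 4 takes a whole SMQ with neither.

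5. **Scale per subject.** Protocol 7.1 plans about 300 subjects at 2:1, which is 300 × 2/3 = 200 on SEP-363856 and 300 × 1/3 = 100 on quetiapine XR. The relapse rate uses the efficacy population, which cannot exceed the number randomized, so these are minimum shifts:
   - SEP-363856: 1/200 = 0.5 percentage points per misclassified subject.
   - Quetiapine XR: 1/100 = 1.0 percentage point per misclassified subject.
   - Five such subjects in one arm, purely as an illustration: 5/200 = 2.5 points or 5/100 = 5.0 points.

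6. **What cannot be computed.** Nothing in the documents says how often these terms lead to withdrawal in either arm. Neither the number of errors nor the direction of any bias can be derived.

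**The case against.** The strongest reply is that silence is not exclusion. A reader might infer that the SAP hands criterion 4 to a program alone. It does not say so. Protocol 15.3.5 still calls for manual review, SAP 3.7 does not withdraw it, and a separate Blinded Data Review Plan, which is not among the documents, might cover it. That limits the claim to a review step that is not named. It does not remove the problem. Where the SAP relies on blinded review it says so: for pooling discontinuation reasons (16.1.1.2), identifying MSQ subjects (16.2.9) and classifying metabolic medications (17.2.3). An analyst following 16.2.12 would count every hit.

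Second, the rule already carries some judgement. Action taken is recorded for the specific AE, and protocol 12.1.1 asks investigators to record a diagnosis rather than its symptoms. Exclusion 2 also keeps several of the listed disorders out at entry. These points make odd hits less likely, but they do not make a withdrawal for new major depression an exacerbation of schizophrenia.

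Third, a fixed search is transparent and reproducible, and SAP 7.4 reports only nominal p-values. Both points are true and both limit the weight of the issue.

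A reader might also point to the many Appendix 13 terms that recur on the drug-abuse list in Appendix 7. That overlap is not evidence here. Most of the shared terms are core psychotic symptoms or diagnoses, such as the hallucination terms, and can be true exacerbations.

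**Conclusion.** The concern holds. Applied as written, the criterion-4 rule can count withdrawals as schizophrenia relapse when their cause is something else. The SAP does not name the review that the protocol calls for, and it records no change. The size is at least about 0.5 points (SEP-363856) or 1.0 point (quetiapine XR) on the relapse rate for each misclassified subject who meets no other criterion, assuming about 200 and 100 randomized.

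A reader might infer that the relapse comparison is biased towards one drug, or that 130 terms imply many false relapses. The documents support neither: they give no event frequencies, and some listed terms are unlikely to arise. All efficacy analyses in this study are exploratory, and the primary endpoint of AEs, SAEs and AEs leading to discontinuation is unaffected. The change should be made before database lock.

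**What to change.** In SAP 16.2.12, state three things:

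- Every Appendix 13 AE with an action taken of Drug Withdrawn receives a documented medical review, blinded to treatment, before database lock. The Blinded Data Review already planned is a natural place for it.
- Only events judged to be an exacerbation of schizophrenia count towards criterion 4.
- Hits that are not counted appear in a listing.

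The review should rest on the CRF data. The first question in SAP 17.1.13, which asks whether a psychiatric AE could be an exacerbation of the underlying mental illness, can serve as supporting information. It is collected for all serious psychiatric AEs and for non-serious ones leading to study discontinuation, but at present it goes to listings only. If the sponsor prefers the fixed search without review, SAP 3.7 should record and justify that departure from the protocol.

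The cost is SAP wording and some blinded review time; no new data collection is needed. There are three drawbacks. A judgement enters the endpoint and must be documented while blinded. The answers to that question sit in trackers outside the CRF, so using them brings non-CRF information into the endpoint. The number of relapse events may also fall.
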